6.1. Primary Objective

The primary objective is to assess the efficacy of LY2951742 300 mg administered every 30 days compared with placebo in reducing the frequency of weekly cluster headache attacks in patients with chronic cluster headache. The primary outcome measure is the weekly cluster headache attack frequency. The primary endpoint is the overall mean change from baseline in weekly cluster headache attack frequency during the 12-week double-blind treatment phase with LY2951742 compared with placebo. The baseline cluster headache attack frequency is based on the last 14 days in the eligibility report (pre-randomization diary phase).

6.2. Secondary Objectives

6.2.1. Gated Objectives

- To assess the efficacy of LY2951742 300 mg compared with placebo in the estimated mean proportion of patients with a 50% or greater reduction from baseline in the weekly frequency of cluster headache attacks during the 12-week double-blind treatment phase.
- To assess the efficacy of LY2951742 300 mg compared with placebo in the proportion of patients meeting sustained response through Week 12. For this analysis, sustained response is defined as a 50% or greater reduction in the weekly cluster attack frequency from baseline to Weeks 3/4 and maintained at Weeks 5/6, Weeks 7/8, Weeks 9/10, and Weeks 11/12.

6.2.2. Other Secondary Objectives

- To assess whether LY2951742 300 mg is superior to placebo on the following:
 - mean change in the weekly cluster headache attack frequency from baseline to each 2-week interval through Week 12
 - the proportion of patients with a 50% or greater reduction in the weekly cluster headache attack frequency from baseline at each 2-week interval through Week 12
 - the proportion of patients with a 30% or greater reduction in the weekly cluster headache attack frequency from baseline at each 2-week interval through Week 12
 - proportion of patients reporting a score of 1 (“very much better”) or 2 (“much better”) on the Patient Global Impression of Improvement (PGI-I) at Month 1, Month 2, and Month 3

- To compare LY2951742 300 mg with placebo on the following safety and tolerability measures:
 - spontaneously reported treatment-emergent adverse events (TEAEs)
 - serious adverse events
 - adverse events leading to discontinuation
 - suicidal ideation and behaviors assessed by solicited questioning using the Columbia-Suicide Severity Rating Scale (C-SSRS).
- To assess the development and consequences of anti-drug antibodies (ADA) to LY2951742 in patients exposed to LY2951742; to provide samples for subsequent evaluation of neutralizing ADA (NAb).
- To evaluate the pharmacokinetics of LY2951742.

6.3. Exploratory Objectives

To assess whether LY2951742 300 mg is superior to placebo as measured by:

- Proportion of patients randomized to LY2951742 meeting “very much better” or “much better” on the PGI-I at Month 9 and Month 15.
- Mean change in the weekly number of times of abortive medication use from baseline to each 2-week interval through Week 12 comparing LY2951742 with placebo.
- Change in percentage of times using oxygen from baseline for each 2-week interval through Week 12 comparing LY2951742 with placebo.
- Change in percentage of times using triptan from baseline for each 2-week interval through Week 12 comparing LY2951742 with placebo.
- Change in percentage of times of using acetaminophen/paracetamol or nonsteroidal anti-inflammatory drugs (NSAIDs) from baseline for each 2-week interval through Week 12 comparing LY2951742 with placebo.
- Responder analyses of LY2951742 compared with placebo from baseline to each 2-week interval through Week 12 for the proportion of patients meeting:
 - a 75% or greater reduction in the weekly cluster headache attack frequency
 - a 100% reduction in weekly cluster headache attack frequency
- Mean change from baseline to each 2-week interval through Week 12 in the cluster headache attack average weekly pain severity based on 5-point pain severity scale comparing LY2951742 with placebo.

© [REDACTED]

C
C
I

[figure not shown]
7. Investigational Plan

7.1. Summary of Study Design

Study CGAM is a Phase 3 multi-center, outpatient, randomized, double-blind, placebo-controlled study of LY2951742 300 mg for the prevention of chronic cluster headache. The study has 5 study phases (SP):

- SP I (screening/washout phase)
- SP II (pre-randomization diary phase)
- SP III (double-blind treatment phase)
- SP IV (optional open-label extension phase)
- SP V (post-treatment follow-up phase)

Figure CGAM 1 illustrates the study design.

Abbreviations: ePRO = electronic patient reported outcome; SP = study phase; X = injection of investigational product.

^a ePRO diary reporting will be completed daily during SP II and SP III. “Day” will be defined on a 24- clock day.

^b Patients begin recording in their diary on a daily basis and call site to schedule Visit 2 and Visit 3.

^c Visit 2 will occur during SP II. The minimum time between Visit 2 and Visit 3 is 5 days.

^d Scheduling of this office visit, Visit 3, should take into consideration that patients must have at least 14 days to record a baseline assessment of cluster headache attack frequency prior to Visit 3.

^e Telephone visit 7 days after office visit only for assessment of spontaneously reported AEs.

Figure CGAM.1. Illustration of study design for clinical protocol I5Q-MC-CGAM.

Study Phase I is the screening/washout phase beginning at Visit 1 to the start of SP II and lasting for a minimum of 0 days to a maximum of 65 days. Patients will sign an informed consent form (ICF) at Visit 1 prior to completing study-related initial screening procedures. At Visit 1, patients will discontinue excluded medications, non-fasting laboratory samples will be collected (fasting laboratory samples are collected at visits indicated in the study schedule), and other additional baseline procedures will be performed to determine further eligibility (see Study Schedule, [Attachment 1](#)).

At Visit 1, for patients who meet initial screening criteria, an ePRO diary may be dispensed to the patient to record his or her daily cluster headache attack information and allowed use of abortive treatments (collectively referred to as ‘daily cluster headache attack information’ throughout the protocol). Visit 1 will be considered complete when the last scheduled procedure of the screening assessment for the patient is completed.

The patient will begin recording in his or her ePRO daily diary only after he or she has completed all Visit 1 screening procedures and wash-out of excluded medications and is experiencing a cluster headache attack. The start of the ePRO daily diary recordings represents the beginning of SP II. If not scheduled, the patient should call the office to schedule Visit 2 and Visit 3. There should be a minimum of 5 days between Visit 2 and Visit 3. The site should ensure the patient has recorded ePRO diary data for at least 14 consecutive days prior to Visit 3 to establish his or her baseline cluster headache attack frequency. Sites may schedule Visit 3 beginning 15 days from the start of SP II.

Beginning fifteen days after the start of SP II, an eligibility report will be available from the ePRO vendor for the investigative site personnel to execute that will determine the patient’s eligibility based on the patient’s ePRO diary data from SP II (refer to the study tool: “Eligibility Determination and Randomization Process” for the full description of valid dates to execute the eligibility report). If the patient is eligible, a blinded randomization authorization code will be listed for the patient. The site personnel, either blinded or unblinded, must log into the Eli Lilly Interactive Web Response System (IWRS) to process the patient’s randomization visit (Visit 3). The site should discontinue the non-eligible patient in the IWRS at Visit 3. For patients that are eligible for randomization, the site should enter the randomization authorization code provided by the vendor.

Only the Unblinded Site Personnel should confirm the assigned packages in IWRS. The Unblinded Site Personnel should store the randomization authorization code from the vendor for each patient in a secure pharmacy record for the study.

Study Phase III is a 12-week randomized, double-blind, placebo-controlled treatment phase. Patients who meet all eligibility criteria will be randomized (1:1) at Visit 3 to 1 of the 2 treatment arms (LY2951742 300 mg or placebo).

For each visit in SP III where a dose is administered, the unblinded site personnel will prepare the IP for each patient. Each dose of IP will be administered as 3 subcutaneous (SC) injections at office Visits 3, 6, and 8. After the first administration of IP at Visit 3, the patient should remain in the office for 30 minutes for observation. The site will have scheduled phone visits

(Visits 4 and 7) with the patient approximately 1 week after the first two IP administration visits during SP III to collect spontaneously reported AEs. At Visit 5, the patient will come into the office for the collection of blood samples 2 weeks after the first dose. During SP III, the patient will continue to record his or her cluster headache attack information daily in the ePRO diary.

- For patients who discontinue early in SP III, they should enter SP V.
- For patients who complete SP III, SP IV is an optional 1-year exposure, open-label treatment phase which is described below.
- For patients who choose not to enter SP IV, they should enter SP V.

During SP IV, the unblinded site personnel will continue to prepare the IP for each patient. All patients who enter SP IV will receive open-label monthly injections of LY2951742. All study procedures at Visit 9 must be completed prior to patients receiving the first dose of LY2951742 in SP IV. Patients and investigators will remain blinded to the SP III treatment assignments during SP IV. Each dose of IP will be administered as 3 SC injections at office visits: Visits 9 and 11 through 21. Since placebo patients will be transitioning to LY2951742 at Visit 9, all patients should remain in the office for 30 minutes for observation after administration of IP. Also, during SP IV, some patients may transition to LY2951742 300 mg supplied in 3 prefilled syringes with each syringe containing 100 mg. These patients should remain in the office for 30 minutes for observation after the first prefilled syringe injection. All patients will continue to record his or her cluster headache attack information daily in the ePRO diary until Visit 11.

Study Phase V is a 16-week post-treatment phase for safety follow-up.

7.2. Discussion of Design and Control

This study is a double-blind, placebo-controlled, multi-center study consisting of 5 SPs: a screening phase, a pre-randomization diary phase to assess cluster headache attack frequency for eligibility, a double-blind, placebo-controlled treatment phase to assess treatment outcomes, an open-label extension phase, and a post-treatment follow-up phase to allow for safety monitoring after LY2951742 treatment is stopped.

The proposed duration of the double-blind treatment phase is 3 months, with the primary endpoint assessed from Weeks 1/2 through Weeks 11/12 after the first IP dose. The length of the randomized, double-blind treatment phase (3 months) is believed to be a sufficient duration to assess the efficacy of a cluster headache prevention medication given the mechanism and observed onset of action for CGRP antibodies in migraine (Dodick et al. 2014a, 2014b). The primary measure of weekly cluster headache attack frequency and use of placebo-control is consistent with current published International Headache Society guidelines (IHS 1995). Moreover, a placebo-controlled study with a duration longer than 3 months may not be tolerated by patients suffering from chronic cluster headache.

Because of the severity of patients suffering from chronic cluster headache, a requirement of patients to washout of all preventive treatments before study entry is not feasible. Therefore, the study allows use of certain allowed preventive treatments during the study as long as the patient

is on a stable dose for at least 2 months prior to the pre-randomization diary phase (SP II) and remains on that dose throughout the study.

8. Study Population

All patients must meet the following selection criteria. Eligibility of patients for study enrollment will be based on the results of a screening medical history, physical examination, clinical laboratory tests, ECG, and cluster headache history during SP I and SP II, as described in the Inclusion and Exclusion Criteria sections below. The nature of any co-morbid conditions present at the time of the physical examination and any pre-existing conditions must be documented.

Individuals who do not meet the criteria for participation in this study (screen failure) may be considered for rescreen once, for selected criteria, with approval from Lilly Medical, as described in Section 8.3.

Prospective approval of protocol deviations to recruitment and enrollment criteria, also known as protocol waivers or exemptions, are not permitted.

8.1. Inclusion Criteria

Patients who meet all of the following inclusion criteria are eligible for enrollment into the study:

- [1] Male and female outpatients 18 to 65 years of age inclusive prior to signing informed consent.
- [2] At Visit 1, patients must have a history of *chronic cluster headache* and distinguished from episodic cluster headache as defined by IHS ICHD-3 beta (ICHD-3 2013) (see Section 8.1.1).
- [3] **Do not share this inclusion criteria with potential patients:** During SP II, have a baseline cluster headache attack frequency (based on ePRO vendor eligibility report) of:
 - [3a] minimum of 8 cluster headache attacks
 - [3b] maximum of 8 cluster headache attacks per day

Note: a patient with 2 or more consecutive days without an attack during the baseline assessment will be excluded.
- [4] For patients on preventive treatment for cluster headache, must be on a stable regimen (with stable dose for at least 2 months prior to the start of SP II), which may include verapamil (maximum daily dosage: 480 mg), lithium, melatonin, valproate, gabapentin, and topiramate. Use of any other preventive treatments for cluster headache is not allowed.
- [5] In the opinion of the investigator, spontaneous remission during the double-blind treatment phase is not anticipated based on the patient's history of cluster periodicity.
- [6] At Visit 1, are able to distinguish cluster headache attacks from other headaches (that is, tension-type headaches, migraine).

- [7] Investigator judges the patient as reliable to follow all study procedures, keep all study visits, and be compliant with study requirements.
- [8] Women of child-bearing potential may participate in the study.
 - [8a] Women of child-bearing potential must test negative for pregnancy (based on a serum pregnancy test) at the time of enrollment and must agree to use a reliable method of birth control during the study and for 5 months following the last dose of IP.
 - [8b] Male patients agree to use a reliable method of birth control during the study and for 5 months following last dose of IP.
 - [8c] Women not of child-bearing potential are those who are infertile due to surgical sterilization (at least 6 weeks after surgical bilateral oophorectomy with or without hysterectomy or at least 6 weeks after tubal ligation) confirmed by medical history, or menopause. Menopause is defined as spontaneous amenorrhea for at least 12 months not induced by a medical condition, or spontaneous amenorrhea of 6-12 months and a follicle stimulating hormone (FSH) level >40 mIU/mL.
- [9] Have not taken any of the following excluded medications or other treatments for cluster headache within the timeframe noted:
 - [9a] use within 14 days prior to SP II of any of the following: dihydroergotamine or ergot derivatives, methergine, opioids
 - [9b] use within 30 days prior to SP II of any of the following: systemic or injected corticosteroids, occipital nerve block, any other cranial or extracranial nerve block, any neurostimulation treatment

Note: Patients will be allowed to use only the following for acute/abortive treatment (treatment initiated at the start of the cluster headache attack to shorten overall attack duration) for their cluster headache attacks: high-flow oxygen, oral triptans, sumatriptan subcutaneous injections, sumatriptan nasal spray, zolmitriptan nasal spray, acetaminophen and NSAIDs.

- [10] Throughout the study (informed consent through Visit 24), agree to refrain from the use of drugs of abuse per United States Federal Guidelines (Schedule I) such as, but not limited to, cannabinoids, cannabis, psilocybin (mushrooms), LSD and 2-bromo-LSD.
- [11] Agree not to post any personal medical data related to the study or information related to the study on any website or social media site (for example, Facebook, Twitter, LinkedIn, Google+, etc.) until the entire trial has completed.
- [12] Have given written informed consent.

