confirmation	A process used to confirm that laboratory test results meet the quality requirements defined by the laboratory generating the data and that Eli Lilly and Company (Lilly) is confident that results are accurate. Confirmation will either occur immediately after initial testing or will require that samples be held to be retested at some defined time point, depending on the steps required to obtain confirmed results.
CRF/eCRF	case report form/electronic case report form: Sometimes referred to as clinical report form: A printed or electronic form for recording study participants' data during a clinical study, as required by the protocol.
CRP/CRS	clinical research physician (CRP): Individual responsible for the medical conduct of the study. Responsibilities of the CRP may be performed by a physician, clinical research scientist (CRS), global safety physician or other medical officer.
C-SSRS	Columbia Suicide Severity Rating Scale
DMC	Data Monitoring Committee
DNA	deoxyribonucleic acid
ECG	electrocardiogram
EDC	electronic data capture system
efficacy	Efficacy is the ability of a treatment to achieve a beneficial intended result under controlled conditions.
end of trial (study)	End of trial is the date of the last visit or last scheduled procedure shown in the Study Schedule for the last [patient/subject].
enroll	The act of assigning a patient to a treatment. Patients who are enrolled in the trial are those who have been assigned to a treatment.
Enter	Patients entered into a trial are those who sign the informed consent form directly or through their legally acceptable representatives.
ePRO	electronic patient reported outcome
ERB/IRB	ethical review board/institutional review board: A board or committee (institutional, regional, or national) composed of medical and nonmedical members whose responsibility is to verify that the safety, welfare, and human rights of the patients participating in a clinical study are protected.
FSH	follicle stimulating hormone
GCP	good clinical practice
HLT	High Level Term
IB	Investigator's Brochure
ICD	informed consent document
ICF	informed consent form

ICH	International Council for Harmonisation
ICHD-3	International Classification of Headache Disorders, Third edition, beta
IHS	International Headache Society

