9.3. Method of Assignment to Treatment

A patient number will be assigned to each patient after the ICF is signed and dated. This identification number must appear on all patient-related documents.

Patients who meet all criteria for enrollment will be randomized to double-blind treatment at Visit 3. Assignment to treatment groups will be determined by a computer-generated random sequence using an IWRS. The IWRS will be used to assign double-blind IP to each patient in SP III and open-label IP in SP IV. The Unblinded Site Personnel should confirm the assigned packages prior to preparation of double-blind IP in SP III.

The IWRS system will be programmed following the dynamic allocation (minimization) method of Pocock and Simon (1975) to balance the treatment arms for the factors of gender, average daily attack frequency (≤ 4 attacks per day, > 4 attacks per day), verapamil (yes/no), and investigative site. The purpose of the algorithm is to maintain approximately the same proportion of gender, verapamil use, and baseline average daily attack frequency in each arm of the study, and to balance (based on the treatment allocation ratio) the number of patients assigned to treatment arms within each investigative site.

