Vital sign	X	X	X		X		X	X		Vital signs will also be taken at unscheduled office visits. Vital signs include body temperature, blood pressure, and pulse. Blood pressure and pulse will be measured in triplicate in the sitting position and should be measured prior to blood draws. Blood pressure will be assessed by utilizing a calibrated machine that will be provided to the sites.
Hematology	X		X					X		
Clinical chemistry ^a	X		X					X		Except for V1, chemistry labs require fasting (no food or drink, except water, for at least 8 hrs).
Urinalysis	X							X		
HbA1C	X							X		

Study Schedule, Protocol I5Q-MC-CGAM: SP I to SP III

Study Phase (SP)	SP I	SP II	SP III							
Description	Screening	Pre-Randomization Diary	Treatment						Comments	
Visit	1	2	3	4 (Phone visit)	5	6	7 (Phone visit)	8	9	Comments
Month						1		2	3	
Serum Pregnancy or FSH	X									Female patients only
Urine drug screen	X									
Randomization			X							
Immunogenicity			X		X	X		X	X	Immunogenicity samples must be collected prior to dose administration if the visit is a dosing visit. Samples will be taken in the event of early termination. The timing of samples will be recorded.
										CCI [REDACTED]
Plasma Storage Sample (K+/EDTA)	X	X	X		X	X		X	X	Samples must be collected prior to dose administration if the visit is a dosing visit. The timing of the samples will be recorded. These samples will be collected in an K+/EDTA container.
PK sampling					X	X		X	X	Samples must be collected prior to dose administration if the visit is a dosing visit. The timing of the samples will be recorded.
CCI [REDACTED]			C							[REDACTED]
RNA storage sample	X	X		X	X		X	X		Sample must be collected in a Tempus tube.

Study Schedule, Protocol I5Q-MC-CGAM: SP I to SP III

Study Phase (SP)	SP I	SP II	SP III							
Description	Screening	Pre-Randomization Diary	Treatment							Comments
Visit	1	2	3	4 (Phone visit)	5	6	7 (Phone visit)	8	9	Phone visits (V4 and V7) are contacts between office visits to collect any spontaneously reported AE after the first two injections of IP.
Month					1			2	3	
PGI-I					X			X	X	
C-SSRS/SHSF, SHFU	X	X	X		X			X	X	Should also be completed at unscheduled office visits.
Recording of AEs	X	X	X	X	X	X	X	X	X	
Review Diary data			X	X		X		X	X	Following Informed Consent, patients will be required to complete their diaries daily beginning the day of their next cluster headache attack. Sites should review the diary compliance with the patient during specified office visits.

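### Criterion 8a asks for a negative serum pregnancy test at enrollment, but the only test scheduled before the first dose is at screening, at least 14 days earlier

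*Protocol*

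**What the plan says.** Criterion 8a (Protocol Section 8.1) states that women of child-bearing potential "must test negative for pregnancy (based on a serum pregnancy test) at the time of enrollment". They must also agree to reliable contraception during the study and for 5 months after the last dose.

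Section 4 defines *enroll* as "The act of assigning a patient to a treatment". It treats *enter* as a different act: "Patients entered into a trial are those who sign the informed consent form directly". Section 9.3 fixes the visit of assignment: "Patients who meet all criteria for enrollment will be randomized to double-blind treatment at Visit 3". Section 7.1 puts the first dose at the same visit: "Each dose of IP will be administered as 3 subcutaneous (SC) injections at office Visits 3, 6, and 8".

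In the Attachment 1 schedule for SP I to SP III, the row "Serum Pregnancy or FSH" is marked at Visit 1 only. Footnote c of Attachment 2 gives the timing independently: at screening, with a reference to inclusion criterion 8, and then at Visits 22 and 24 and at early termination. Neither place lists Visit 2 or Visit 3.

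**The concern.** Read with the protocol's own definitions, criterion 8a calls for a negative result at Visit 3, and the schedule does not produce one. Section 8 does not permit waivers of enrollment criteria, so sites need a criterion that the schedule lets them meet as written.

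The wording matters less than what follows from it. A woman who conceives after the Visit 1 sample, or whose pregnancy was too early to detect then, could be randomized and dosed without any required test to show it. The protocol treats exposure in pregnancy as something to avoid: exclusion 21 bars pregnant women, and contraception must continue for 5 months after the last dose.

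**Working it through.** No sample size, power or error-rate figure is involved, and the plan states no figure for this gap to reproduce. The check has two parts: the timing of the test, and the length of the interval.

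**Timing of the test**

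| Item | Source | Visit |
|---|---|---|
| Negative serum test required at enrollment | Protocol 8.1, criterion 8a | Visit of enrollment |
| Enrollment is treatment assignment | Protocol 4 | Visit of assignment |
| Assignment | Protocol 9.3 | Visit 3 |
| First dose | Protocol 7.1 | Visit 3 |
| Scheduled tests up to the first dose | Attachment 1; Attachment 2, footnote c | Visit 1 only |

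The Attachment 1 table is partly broken in the text available, but the result does not depend on it, because footnote c lists the visits separately. Criteria 2 and 6 in the same list name Visit 1 when they mean screening. Criterion 8a does not.

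**Length of the interval**

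Inputs:
- SP I, from Visit 1 to the first diary day: 0 to 65 days (Section 7.1 and Attachment 1).
- Order of events: "The patient will begin recording in his or her ePRO daily diary only after he or she has completed all Visit 1 screening procedures" (Section 7.1).
- Diary days before randomization: "The site should ensure the patient has recorded ePRO diary data for at least 14 consecutive days prior to Visit 3" (Section 7.1).
- Earliest Visit 3: 15 days from the start of SP II (Section 7.1).
- SP II: 14 to 17 days, in a cell of Attachment 1 labelled as a minimum time.

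Formula: gap from test to first dose = days from the sample to the first diary day + days from the first diary day to Visit 3.

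- Shortest: 0 + 14 = 14 days. Taking the 15-day scheduling rule as elapsed days gives 0 + 15 = 15. If the first diary day counts as day 1, a visit on day 15 is 15 − 1 = 14 days later. Either way the gap is at least 14 days.
- Long case, with the sample drawn on the first day of Visit 1: 65 + 14 = 79 days and 65 + 17 = 82 days.
- If Visit 1 procedures are spread over several days, a later draw shortens the gap. It cannot fall below 14 days, because the diary starts only once those procedures are done.
- Pregnancy tests scheduled between the first diary day and the first dose: 0.

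**The next scheduled test**

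For a patient who goes through the open-label phase, it is Visit 22 (Day 450). With Visit 3 as Day 1, that is 450 − 1 = 449 days after the first dose. Section 9.5 gives 3 doses in SP III and 12 in SP IV, so 3 + 12 = 15 doses come before it. A test comes sooner only if the early-termination visit applies, or if the patient skips the extension and reaches Visit 24 through follow-up.

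**The case against.** The strongest reply is that the instruction to sites is clear. Footnote c ties the screening test to criterion 8, and Section 8 bases enrollment eligibility on laboratory tests done in SP I and SP II. The word *enrollment* is also used loosely elsewhere: Section 8.3 uses it for the recruitment period. On this view criterion 8a is badly worded and nothing more. That stands as an account of intent. A reader might infer that the sponsor planned a Visit 3 test and forgot to schedule it, or that every site will knowingly breach the criterion. Footnote c does not support either inference.

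A reader might also infer that nothing protects against dosing a pregnant woman. The documents do not support that. The contraception agreement is a mandatory, preventive entry condition that covers the interval before dosing. Exclusion 21 applies to every patient, and Attachment 1 schedules an eligibility recheck at Visits 2 and 3. Other provisions are weaker: extra safety samples are allowed but not required (Attachment 4, footnote a), and pregnancies during exposure are reported after the fact (Section 10.2.1). None of these, mandatory or not, obliges anyone to run a test before the first dose, so the recheck at Visit 3 has no new pregnancy result to look at.

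Two practical objections also stand. Laboratory data go through a central vendor (Section 11.1) and no turnaround time is given, so a serum result on the day of Visit 3 cannot be assumed. And SAP Appendix 2 already lists a positive pregnancy test under Safety without a visit limit, besides the eligibility entry for a positive serum test before Visit 3. A positive result at Visit 3 would already be captured.

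**Conclusion.** The point holds as a mismatch between criterion 8a and the schedule, together with a real but modest safety gap that rewording would not close. The last required test precedes the first dose by at least 14 days, and by about 79 to 82 days when SP I runs its full 65 days and the sample is drawn on the first day of Visit 1.

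The 82 days should not be read as a maximum, because the 17 comes from a minimum-time entry. Nor should the long case be read as typical: SP I may last 0 days, and the documents give no usual length. They also give no count of women of child-bearing potential and no conception rate, so the number of exposed pregnancies cannot be estimated.

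This is a matter of patient safety and internal consistency. It does not bear on sample size, power, type I error or the primary analysis.

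**What to change.** - Keep the serum test at screening.
- For women of child-bearing potential, require a negative urine pregnancy test before randomization and dosing at Visit 3, or a serum test if its result is available in time.
- Reword criterion 8a to name both tests and their visits, and to allow urine at Visit 3.
- Add the test to the Visit 3 column of Attachment 1 and to footnote c of Attachment 2.
- In SAP Appendix 2, add a missing pre-dose pregnancy test as an important deviation. No other SAP edit is needed, since a positive test is already listed.

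A serum test at Visit 2, at least 5 days before Visit 3, would leave time for a central result and shorten the gap, but it would not reach the day of dosing. Changing criterion 8a to say screening would make the text consistent and leave the gap as it is.

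The cost is one inexpensive test per woman of child-bearing potential, at a visit that already has blood draws and an eligibility recheck, plus a short protocol amendment and one line in the SAP.
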